5.4 Harms

Adverse Event Reporting

- Expected Serious Adverse Events (eSAE). These events have been defined a priori and are being collected and reported as study outcomes and as such will not be labelled nor reported a second time as serious adverse events.
- Unexpected Serious Adverse Events (uSAE). All uSAEs are to be brought to the attention of the site PI (following site specific standard operating procedures). Causality of the uSAE should be adjudicated by the site PI. All possibly or related uSAEs are to be reported in the

Data Collection Forms (both study arms) as described in this section:

o Monitoring and reporting should begin on the first day of study intervention and continue until either:

- the uSAE has been resolved
- 48 hours post study medication stop or death whichever occurs first
- if the uSAE remains ongoing at 3 months it will be reported as such

o Supporting source documentation of all reported uSAEs must be submitted for additional and final central adjudication.

o Abnormal laboratory results do not need to be recorded unless considered by the investigator to be relevant in terms of subject or trial safety (or in relation to a serious adverse event that is being reported).

 CHU ANGERS <small>CENTRE HOSPITALIER UNIVERSITAIRE</small>	 Statistical analysis plan	N° Eudract 2019-002145-37 CT Number : 2024-515994-83-00 SAP V1.0 Date : 15/01/2026
---	--	---

- Serious Adverse Event Reporting. All reportable unexpected SAEs must be reported to the Coordinating Centre within 24 hours of the site's knowledge of the unexpected SAE. The Study Chair and/or Study Steering Committee will review all unexpected SAE's received from the sites. If an unexpected SAE is confirmed, a document summarizing the SAE will be distributed to participating sites. Sites should follow the guidelines of their local REB with respect to the submission of SAEs that occur at the site as well as SAE Notifications.
- All reportable unexpected SAEs will be described with the presentation of the main results

 CENTRE HOSPITALIER UNIVERSITAIRE	 Statistical analysis plan	N° Eudract 2019-002145-37 CT Number : 2024-515994-83-00 SAP V1.0 Date : 15/01/2026
--	---	---

	Main analysis	Sensitivity analyses for the main analyses	Additional analyses	Adjustement**
Primary outcome				
mRS at 3 month	Log-binomial logistic regression with fixed effects for treatment and, and a random effect for center, initial WFNS (<3 or ≥ 3) and patient's consciousness, reported as a risk ratio with 95% CI	
 Another model adjusted with level of consciousness and delay before performing arteriography (< or \geq 12h) Sub-group analysis Per protocol analysis† Patients without missing data 	
 Proportional odds analysis using the Brant-Wald test 	
 center, initial WFNS (<3 or ≥ 3) patient's consciousness at inclusion
Secondary outcomes				
mRS at 6-months	Log-binomial logistic regression reported as a risk ratio with 95% CI		
 unadjusted model Proportional odds analysis using the Brant-Wald test 	
 center, initial WFNS (<3 or ≥ 3) patient's consciousness at inclusion
GOSE at 3 and 6 months	Linear logistic regression model, reported as mean difference with 95% CI		
 unadjusted model 	
 center, initial WFNS (<3 or ≥ 3) patient's consciousness at inclusion
EQ-5D	Linear logistic regression model, reported as mean difference with 95% CI	
 Excluding deceased patient 	
 unadjusted model 	
 center, initial WFNS (<3 or ≥ 3) patient's consciousness at inclusion
Mortality hospital	Log-binomial logistic regression reported as a risk ratio with 95% CI		
 unadjusted model 	
 center, initial WFNS (<3 or ≥ 3) patient's consciousness at inclusion
Mortality 6 months	
 Kaplan-Meier curves and Cox regression hazard ratios 		
 unadjusted model 	
 center, initial WFNS (<3 or ≥ 3) patient's consciousness at inclusion
Tertiary outcomes				
ICU and Hospital LOS	Presented as median difference with 95% CI, using quantile regression		
 median with IQR unadjusted model 	
 center, initial WFNS (<3 or ≥ 3) patient's consciousness at inclusion
Percentage of patients alive and at home at 3 and 6 mnths	Presented as median difference with 95% CI, using quantile regression		
 median with IQR unadjusted model 	
 center, initial WFNS (<3 or ≥ 3) patient's consciousness at inclusion
DAAH90	Presented as median difference with 95% CI, using quantile regression		
 median with IQR unadjusted model 	
 center, initial WFNS (<3 or ≥ 3) patient's consciousness at inclusion
Angiographic success at D7 and D14	Ordinal logistic regression model		
 unadjusted model 	
 center, initial WFNS (<3 or ≥ 3) patient's consciousness at inclusion

 CHU ANGERS <small>CENTRE HOSPITALIER UNIVERSITAIRE</small>	 Statistical analysis plan	N° Eudract 2019-002145-37 CT Number : 2024-515994-83-00 SAP V1.0 Date : 15/01/2026
---	--	---

Number of therapeutic angiography	Presented as median difference with 95% CI, using quantile regression		
 Median with IQR unadjusted model 	
 center, initial WFNS (<3 or ≥3) patient's consciousness at inclusion
volume of cerebral necrosis on MRI done between 3 and 6 months	Presented as median difference with 95% CI, using quantile regression		Median with IQR	
Proportion of patient with hemodynamic intolerance (i.e. introduction of catecholamine or increase of ≥50% of infusion rate) within 24 hours of study medication	Log-binomial logistic regression reported as a risk ratio with 95% CI		
 unadjusted model 	
 center, initial WFNS (<3 or ≥3) patient's consciousness at inclusion
Proportion of patients with dysnatraemia	Log-binomial logistic regression reported as a risk ratio with 95% CI		
 unadjusted model 	
 center, initial WFNS (<3 or ≥3) patient's consciousness at inclusion
Daily dose of catecholamine	Presented graphically with 95% CI, per group			
Daily minimum and maximum natremia	Presented graphically with 95% CI, per group			
Daily urine output	Presented graphically with 95% CI, per group			

Unless otherwise stated, all analyses will be conducted on the Intention to treat population: includes all aSAH patients randomized.

** Adjustments for all listed analyses unless otherwise specified

† Per-protocol population includes the intention to treat population, but excludes those who had a protocol violation.

CI – confidence interval; DAAH – days alive at home at D90; EQ-5D- EuroQOL 5 dimensions; GOSE Glasgow outcome scale extended; ICU – Intensive Care Unit; IQR – Interquartile Range; mRS – modified Rankin Scale; WFNS – World Federation of Neurological Surgeon

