1.2 Objectives

1.2.1 Primary objective

The primary objective of this study is to evaluate the effect of intravenous milrinone infusion, as compared with placebo, on functional neurological outcomes at 3 months in patients with arterial vasospasm following acute aSAH.

1.2.2 Secondary objectives:

To evaluate the effect of IV milrinone vs placebo on a) 3 and 6 months overall function; b) 3- and 6-months quality of life, c) mortality.

 CHU ANGERS <small>CENTRE HOSPITALIER UNIVERSITAIRE</small>	 MiVAR Statistical analysis plan	N° EudraCT 2019-002145-37 CT Number : 2024-515994-83-00 SAP V1.0 Date : 15/01/2026
---	--	---

1.2.3 *Tertiary objectives:*

To evaluate the effect of IV milrinone vs placebo on the intensive care unit (ICU) and hospital length of stays, on angiographic success at D7 and D14 (if available), on cerebral necrotic volume assess by magnetic resonance imaging (MRI) between 3 and 6 months following aSAH (if available) and on adverse events.

2 Section 2: Study Methods

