2.5 Timing of outcome assessment

2.5.1 Primary outcome:

- a) Modified Rankin Scale (mRS) score [3 months]

2.5.2 Secondary outcomes:

- a) Modified Rankin Scale (mRS) score [6 months]; Glasgow Outcome Scale Extended (GOSE) [3 & 6 months]
- b) EuroQOL Quality of Life Scale 5-Dimension 5-Level (EQ-5D-5L) [6 months]
- c) Mortality [in hospital and 6 months]

2.5.3 Tertiary outcomes:

- a) ICU and hospital length of stays [in hospital]
- b) Angiographic success on CTA [D7 and D14 (if available)]
- c) Number of therapeutic arteriography [D14]
- d) Cerebral necrotic volume assess by magnetic resonance imaging (MRI) between 3 and 6 months following aSAH [6 months]
- e) Adverse events [study medication infusion, maximum 14 days]

 CHU ANGERS <small>CENTRE HOSPITALIER UNIVERSITAIRE</small>	 Statistical analysis plan	N° EudraCT 2019-002145-37 CT Number : 2024-515994-83-00 SAP V1.0 Date : 15/01/2026
---	--	---

3 Section 3: Statistical Principles

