4.1 Eligibility

Patients hospitalized for acute aSAH will be included if a cerebral vasospasm occurred, suspected because of a clinical deterioration and/or high blood flow velocity on TCD examination and confirmed by CTA. The inclusion /randomization will be done within 6 hours after vasospasm diagnosis (i.e., when the study investigator get the information, sometimes after re-analysis of the CTA by an expert). Inclusion and exclusion criteria are presented below:

4.1.1 *Inclusion criteria:*

- Adult patients hospitalized for aneurysmal aSAH
- First episode of vasospasm, with a diagnosis confirmed on CTA
- Delay between diagnosis of vasospasm and inclusion \leq 6 hours
- Informed consent from the patient, a legal representative or emergency procedure

4.1.2 *Exclusion criteria:*

- Initial Glasgow score at 3 with a bilateral mydriasis
- Moribund patient
- Contraindication to Milrinone
- Cerebral infarction in the vasospasm area already present on the CT-scanner at the time of diagnosis (lack of expected benefit of treatment in this case according to medical judgement)
- Cardiac failure requiring inotrope administration at the time of randomisation
- Uncontrolled elevated intra-cranial pressure (i.e. ICP>25 mmHg for more than 20 minutes)
- Patient with flutter or cardiac arrhythmia (atrial fibrillation) poorly tolerated

 CHU ANGERS <small>CENTRE HOSPITALIER UNIVERSITAIRE</small>	 Statistical analysis plan	N° EudraCT 2019-002145-37 CT Number : 2024-515994-83-00 SAP V1.0 Date : 15/01/2026
---	--	---

- Major metabolic disturbance (uncorrected hypokalaemia <3 mmol/L)
- Non-affiliation to French health care coverage
- Pregnant, breastfeeding or parturient woman
- Adult deprived of their liberty by judicial or administrative decision
- Adult under compulsory psychiatric care
- Adult patient protected under the law (guardianship or trusteeship)
- Inclusion in an interventional study using Milrinone, or evaluating a treatment of cerebral vasospasm or with the same primary endpoint (mRS at 3 months)

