- b) Percentage of patients alive and at home at 3 and 6 months. It will also be analyzed as the number of days alive and at home at day 90 (DAAH90).
- c) angiographic success will be assessed by the evaluation of vasospasm severity on inclusion, D7 and D14 (if available) CTA. Vasospasm will be quantified according to the reduction of cerebral arteries diameter evaluated on a semi-quantitative scale as: absent, light, mild, moderate or severe, (compared to the diameter measured on admission CTA).
- d) Number of therapeutic arteriography
- e) The volume of cerebral necrosis will be measured on magnetic resonance imaging (MRI) obtained between 3 and 6 months following aSAH
- f) on adverse events evaluated until 48 hours after study medication stop.
- g) The treatment tolerance will be evaluated by assessing the rate of patients with hemodynamic intolerance defined as the need for catecholamines introduction or doses increased by 50% within the first 24 hours of study medication infusion ; and of metabolic intolerance defined as the rate of patients with dysnatremia, (ie natremia<135 mmol/L or >155 mmol/L) occurring during the administration of study medication.

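### Adverse events are a named tertiary outcome without a planned analysis, and the reporting rules in 5.4 allow some serious events to fall outside any comparison between arms

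*SAP*

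**What the plan says.** **Objective and outcome.** Section 1.2.3 lists the effect of milrinone versus placebo on MRI necrotic volume "between 3 and 6 months following aSAH (if available) and on adverse events" among the tertiary objectives. Section 2.5.3 e) repeats the outcome with its window: "Adverse events [study medication infusion, maximum 14 days". Section 5.1.3 f) gives it again with another window: "on adverse events evaluated until 48 hours after study medication stop".

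**Expected serious events.** Section 5.4 states that these were defined in advance, that they "are being collected and reported as study outcomes and as such will not be labelled nor reported a second time as serious adverse events".

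**Other serious events, not on the expected list.** Section 5.4 states: "Causality of the uSAE should be adjudicated by the site PI". It continues: "All possibly or related uSAEs are to be reported in the" data collection forms, for both arms. The promised output is: "All reportable unexpected SAEs will be described with the presentation of the main results".

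**The concern.** An outcome named in the objectives and in both outcome lists should have a stated analysis, and this one has none. Section 5.4 then narrows what could be analysed. Expected serious events leave the serious-adverse-event count on the premise that they appear as study outcomes, but the SAP does not say which outcomes carry them. Unexpected serious events pass a causality judgement before they are recorded.

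In a randomised, blinded, placebo-controlled trial, the comparison of all serious events between arms is the most direct evidence on harm, and it needs no judgement about cause in individual patients. If events are left out before that comparison, the harms section can look more reassuring than the data would justify.

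**Working it through.** No figure in the SAP bears on this point, so the check follows the adverse-event outcome through the document.

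**Step 1: does each tertiary outcome have an analysis?** The seven items of 5.1.3 against 5.2.3 and Table 1:

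| 5.1.3 item | Method in 5.2.3 | Row in Table 1 |
|---|---|---|
| a) ICU and hospital stay | hospital stay only | yes |
| b) alive and at home, DAAH90 | yes | yes |
| c) angiographic success | yes | yes |
| d) therapeutic arteriographies | yes | yes |
| e) MRI necrosis volume | no | yes |
| f) adverse events | **no** | **no** |
| g) treatment tolerance | yes | yes |

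Six of the seven items have a row in Table 1. Item f) is the only one with neither a row nor a method. Tolerance is a separate item, g), so its rows do not stand in for f).

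**Step 2: which harms are compared between arms?**
- Mortality: Cox models in 5.2.2; in Table 1, a risk ratio for hospital mortality and Cox regression for 6-month mortality.
- Hemodynamic intolerance: catecholamines started, or the dose raised by 50%, within the first 24 hours of study drug (5.1.3 g). Logistic model in 5.2.3, risk ratio in Table 1.
- Dysnatraemia: natremia below 135 or above 155 mmol/L during study drug. Logistic model in 5.2.3, risk ratio in Table 1.

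Daily catecholamine dose, natremia and urine output are also plotted by group. Of the three compared outcomes, only death is serious by definition. One of the others covers the first 24 hours, although infusion can last up to 14 days (2.5.3 e), and the other is a laboratory threshold.

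**Step 3: where does a serious event go under 5.4?**

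| Event | Rule in 5.4 | Compared by arm? |
|---|---|---|
| Expected, and one of the three outcomes in step 2 | carried as an outcome | yes |
| Expected, any other kind | not labelled as a serious adverse event | no analysis stated |
| Unexpected, judged possibly related or related | on the forms, then described | no comparison or effect measure stated |
| Unexpected, judged unrelated | not required on the forms | no, unless it is fatal or meets an outcome in step 2 |

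The SAP does not define reportable separately. The causality criterion is the only one given, so the table reads it that way. Central adjudication in 5.4 applies to reported events and cannot recover those never reported.

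**Step 4: the window.** In 2.5.3 e) it ends with infusion, at most 14 days. In 5.1.3 f) it runs 48 hours past the stop. For a patient infused for the full 14 days, the two end at day 14 and at 14 + 2 = day 16. They disagree by 48 hours for every patient stopped by day 14, and the SAP does not say which governs the analysis.

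**The case against.** **The expected list may be in the protocol.** This is fair. The protocol is not at hand, and the absence of the list from the SAP is not an error. The list might consist only of events covered by the three compared outcomes, and then nothing is lost through that route. What stands is that the SAP fixes the analyses and does not make the link. Even in that best case, adverse events still have no analysis, and unrelated unexpected events are still not required on the forms.

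**A general rule may cover it.** Section 5.2 says that patient assessments are described by arm, with percentages compared by chi-square tests, and 4.2 says that safety data of patients who withdraw after randomisation are analysed. Neither names the adverse-event outcome or gives an effect measure. Section 3.1 confines p-values to primary and secondary outcomes, so for a tertiary outcome the general rule leaves little more than percentages. No rule of analysis can restore events that were not recorded.

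**Blinding protects the comparison.** This is largely right. Physicians are blinded, the forms cover both arms, and reported events go to central adjudication. The causality filter should act similarly in both arms, so its main effect is under-ascertainment.

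**Stronger readings.** A reader might infer that no harm outcome is analysed at all, or that the adverse-event objective cannot be answered. The SAP does not support either: mortality and two tolerance outcomes are compared by arm, and related unexpected events are described. Nor does it support saying that the expected harms certainly go uncompared, because the list is not shown.

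**Conclusion.** The point holds as a gap in the analysis of a tertiary outcome, made worse by the reporting rules. Followed as written, the SAP yields comparisons of mortality, 24-hour hemodynamic intolerance and dysnatraemia, and a description of related unexpected serious events. It plans no comparison of all serious adverse events by arm, so the objective is only partly answerable.

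The size in patients is unknown: the SAP gives no serious-event rates and no share of events expected to be judged unrelated. The conclusion rests on two readings. One is that reportable means possibly related or related. The other is that the outcomes said to carry expected events are those listed in the SAP. The primary and secondary analyses are not affected.

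**What to change.** 1. Add to 5.2.3 and Table 1 an adverse-event analysis by arm: patients with at least one recorded serious adverse event, expected and unexpected together and regardless of causality, and patients with each pre-defined expected category. Give risk differences with 95% CIs and no p-values, in line with 3.1. Show related unexpected events as a subset.
2. State the denominator. Section 3.3 leaves patients who withdrew consent out of the ITT population, while 4.2 keeps their safety data.
3. In 5.4, state which analysed outcome carries each expected category, and that not reporting these events a second time does not remove them from the harms tables.
4. Where unrelated unexpected events were not recorded, say so as a limitation next to the table.
5. Reconcile the adverse-event window between 2.5.3 e) and 5.1.3 f).

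The cost is one more table and a longer harms section. According to 5.4 the expected events are already being collected. Section 2.4 places publication of the SAP before database lock, and unblinding after the primary and secondary analyses, so the change can still be made without knowledge of results by arm. The table cannot recover unrelated events that sites never recorded, so it would remain incomplete in that respect.

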2.1 Trial Design

MiVAR is a multi-center, double blinded, randomized, placebo-controlled trial that compares the effect of IV milrinone vs placebo (saline), started within 6 hours of the vasospasm confirmation using an computed tomography angiography (CTA), on 3-months function outcomes, in patients with cerebral vasospasm following aSAH.

2.1.1 *Trial interventions*

Eligible patients are randomly assigned to receive either milrinone or placebo within 6 hours after confirmation of the vasospasm diagnosis on a CTA. Study medications are prepared by unblinded nurses or pharmacists not involved in patients care. The study drugs are diluted according to the patient's body weight, so that infusion rates are identical in the two groups for all patients (i.e. an infusion rate of 10 ml per hour corresponds to 0.1 µg/kg/min of milrinone). Milrinone and saline solution are identical in appearance, thereby ensuring blinding of patients, nurses, physicians and outcome assessors.

- **Milrinone group:** milrinone is administered intravenously as a bolus of 0.1 mg/kg over 30 minutes followed by a continuous infusion at a rate of 1 µg/kg/min. In the absence of improvement, the infusion rate may be increased to 1.5 µg/kg/min.
- **Placebo group:** placebo (normal saline) is administered intravenously at the same infusion rate as milrinone.
- **Both groups:** in both groups, induced hypertension with norepinephrine is recommended, along with maintenance of normovolemia. Oral nimodipine is also recommended through D21 after aSAH. Persistence of vasospasm should be assessed at least twice daily by clinical evaluation and/or transcranial doppler (TCD)

 CHU ANGERS <small>CENTRE HOSPITALIER UNIVERSITAIRE</small>	 Statistical analysis plan	N° EudraCT 2019-002145-37 CT Number : 2024-515994-83-00 SAP V1.0 Date : 15/01/2026
---	--	---

examination. In absence of improvement, arteriography for mechanical and/or pharmacological dilatation is recommended.

Duration of treatments

- Study drug weaning is initiated after 48 hours of infusion, with gradual dose tapering in decrement of 0.5 µg/kg/min steps), once vasospasm is controlled. Study medication is discontinued after 7 days in absence of effect on the D7 CTA or on D14.

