5.2 Analysis Methods

Unless otherwise specified, all analyses will be completed on the intention to treat population.

 CHU ANGERS <small>CENTRE HOSPITALIER UNIVERSITAIRE</small>	 Statistical analysis plan	N° EudraCT 2019-002145-37 CT Number : 2024-515994-83-00 SAP V1.0 Date : 15/01/2026
---	--	---

The characteristics at inclusion and the measures of patient assessments for each treatment arm will be described using percentages or means, standard deviations, medians and interquartile ranges, and compared using Khi-square tests or Student t tests for respectively categorical and continuous data. A summary of the proposed analyses is presented in Table 1.

5.2.1 Primary Outcome:

Primary analysis:

The main statistical analysis will be performed on the intention to treat population using a binomial logistic regression model including as covariates the treatment arm and the different stratification factors for randomization (the center, the initial WFNS score dichotomized as <3 vs ≥ 3 and the patient's consciousness at inclusion).

Secondary analysis:

As a secondary analysis, we will report absolute risk reduction using a proportional odds approach, using the Brant-Wald test at the alpha level of 5%, which may be more sensitive for detecting a shift over the entire spectrum of outcome (mRS 7-point ordinal scale).

Sensitivity analysis:

An other model will be proposed based on the ITT population, including in addition to the covariates already considered the level of consciousness and the delay before performing angiography (within 12 hours or not), and the interactions between these two covariates and the treatment arm, to assess a possible variation in the treatment effect according to the status on these two covariates

These two models will be performed on the per-protocol population as an evaluation of the robustness of their results. In any cases, the primary analysis results will be authoritative.

5.2.2 Secondary Outcomes:

- The analysis of the mRS, the extended GOS and the EQ-5D score at 3 and 6 months will be performed considering (ordinal) proportional odds models, based on the same set of covariates.
- The ICU mortality and 6 months mortality will be analyzed using Cox models based on the same set of covariates. The validation of these models will be evaluated by analyzing Schoenfeld residuals.

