 CHU ANGERS <small>CENTRE HOSPITALIER UNIVERSITAIRE</small>	 Statistical analysis plan	N° EudraCT 2019-002145-37 CT Number : 2024-515994-83-00 SAP V1.0 Date : 15/01/2026
---	--	---

5.2.3 *Tertiary outcomes*

- The analysis of angiographic successes at day 7 and 14 will be performed considering (ordinal) proportional odds models, based on the same set of covariates
- The proportion of therapeutic arteriography between each group and the median number of arteriography will be compared.
- The analysis of hospital length of stay will be carried out by using linear regression models based on the same set of covariates.
- Patients outcomes and treatment tolerance will be analyzed using logistic models for dichotomous data (transfer to a convalescent center, patients living at home at 3 and 6 months, need to initiate or to increase the catecholamine doses by 50%, occurrence of dysnatremia), or linear regression models for continuous data (DAAH90, daily dose of catecholamines, average daily urine output).

5.2.4 *Pre-planned sub-group analysis*

We plan exploratory subgroup analyses for the primary outcome (as described above) in the following sub-groups:

- Sex: female sex versus male sex. We hypothesize no treatment effect difference between male and female sex.
- Initial WFNS score <3 vs ≥ 3 . We hypothesize that the treatment effect is more important in the less severe patients (WFNS <3).
- Consciousness level at inclusion: conscious vs unconscious. We hypothesize that the treatment effect is more important in the less severe patients (conscious patients).

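### Table 1 analyses 6-month mRS with a centre-adjusted log-binomial model and no fallback; the solution can often lie on the boundary, where ordinary fitting may fail and the Wald interval is not valid

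*SAP*

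**What the plan says.** Table 1 gives the main analysis of 6-month mRS as "Log-binomial logistic regression reported as a risk ratio with 95% CI". The same entry stands for hospital mortality and for two tolerance outcomes, "Proportion of patient with hemodynamic intolerance" and "Proportion of patients with dysnatraemia". In each row the adjustment column lists centre, WFNS (below 3 or not) and consciousness at inclusion, and a footnote makes this general: "Adjustments for all listed analyses unless otherwise specified". An unadjusted model appears only as an additional analysis.

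Only the primary-outcome row says how centre enters the model: "and a random effect for center, initial WFNS". The four rows above do not say whether centre is fixed or random.

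The text names other models for the same outcomes. Under section 5.2.2, the analysis of mRS at 3 and 6 months "will be performed considering (ordinal) proportional odds models, based on the same set of covariates". The same section plans Cox models for death in ICU and to 6 months, where Table 1 has hospital mortality. Section 5.2.3 says that "treatment tolerance will be analyzed using logistic models for dichotomous data".

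Section 2.1 states that "MiVAR is a multi-center, double blinded, randomized, placebo-controlled trial", but the number of centres is not given. Nor are expected rates for the tolerance outcomes or hospital death. The SAP has no alternative if the log-binomial fit fails, and no rule for small centres.

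**The concern.** Under a log link the treatment effect multiplies the risk in every covariate cell, and nothing stops the product from exceeding 1. The cells most exposed are those with the best prognosis (low WFNS grade, conscious) in centres with high observed rates. If the likelihood keeps rising up to the point where some fitted probability equals 1, the maximum lies on the edge of the parameter space. Standard iterative fitting may then not converge, and the Wald interval, which assumes an interior maximum, loses its justification.

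The 6-month mRS is a secondary outcome, so under section 3.1 it receives a p-value. If its prespecified model fails, the analyst must drop centre, merge centres or change the link after seeing outcome data. Section 5.3 plans at least ten imputations, and the model must fit in each of them before pooling.

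**Working it through.** **Planning figures (section 2.3).** With rates 0.35 and 0.50, two-sided 5% and 80% power:

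n per arm = [1.96·√(2·0.425·0.575) + 0.8416·√(0.35·0.65 + 0.50·0.50)]² / 0.15² = (1.370 + 0.582)² / 0.0225 = 169.3, so 170 per arm and 340 in all, as stated. Then 340/0.95 = 358, which the SAP rounds to 360. The sample size is not in question.

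**Where the limit lies.** 0.50/0.35 = 1.43 and 1/1.43 = 0.70. At this risk ratio, a cell with a control rate above 70% would need a rate above 100% under milrinone.

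**Why centre matters.** Suppose odds ratios of 3 for WFNS and for consciousness (an assumption). A log-binomial fit without centre then gives the best cell a fitted probability of 0.77, which leaves room. A centre reaches the limit when its rate is 1/0.77 = 1.30 times the average. As a rough guide, the average rate is (0.35 + 0.50)/2 = 0.425:
- 15 equal centres, 360/15 = 24 patients each: standard error √(0.425·0.575/24) = 0.101, or 24% of the rate. A 30% excess is about 1.3 standard errors.
- 5 equal centres, 72 patients each: standard error 0.058, or 14%. A 30% excess is about 2.2 standard errors.

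Chance variation between centres can therefore reach the limit once there are many centres.

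**Simulation at 35% vs 50%, centre fixed.** Entries are the share of trials with no interior solution. Sets A to D use equal centres; A and B have 342 patients (360 × 0.95). Strong covariates there are odds ratios 0.40 (WFNS) and 0.35 (unconscious) with centre SD 0.4 on the logit scale; weak are 0.6, 0.6 and 0.2. Set E has 360 patients, unequal centres, odds ratios of 3 and SD 0.3 (weak: 1.5 and 0.2). Trials per scenario: A 100, B 60, C 40, D not recorded, E 150.

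| Covariates | Set | 5 centres | 8 | 10 | 15 | 20 | 25 | 30 |
|---|---|---|---|---|---|---|---|---|
| Strong | A | – | 37% | – | 87% | – | 100% | – |
| Strong | B | 17% | 55% | – | 97% | – | 100% | – |
| Strong | C | – | 53% | – | 88% | – | 100% | – |
| Strong | D | 22% | 64% | – | 90% | – | 100% | – |
| Strong | E | 35% | – | 75% | – | 99% | – | 99% |
| Weak | A | – | 4% | – | 36% | – | – | – |
| Weak | B | 0% | 10% | – | 42% | – | 78% | – |
| Weak | D | 4% | 14% | – | 28% | – | 76% | – |
| Weak | E | – | – | 26% | – | 79% | – | – |

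With 40 trials the Monte Carlo standard error is at most √(0.25/40) = 8 percentage points. In set E a standard GLM routine failed at similar rates under strong covariates: 35%, 70%, 95% and 99%. Without centre in the model the share is 0%.

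**Random centre effect.** With a log-scale random effect, boundary solutions occurred in 0% to 5% of trials at SD 0.1 and in 35% to 63% at SD 0.2 (40 trials each). A direct calculation points the same way. With ln 0.77 = −0.26, a centre SD of 0.15 gives P(Z > 0.26/0.15) ≈ 4%, and SD 0.20 gives about 10%, of centres above probability 1 in the best cell.

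**Lower event rates.** Equal centres at 15% to 20% gave 0% to 5%. Unequal centres at 20% in both arms gave 2%, 19%, 59% and 89% for 5, 10, 20 and 30 centres; at 10% vs 15% they gave 2%, 6%, 45% and 67%.

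**The alternative.** Logistic regression standardised to a risk ratio, with delta-method standard error, gave finite and plausible results in every trial up to 25 centres. Modified Poisson regression with robust errors, dropping centres with no event, also gave a finite risk ratio (about 1.4, log-scale SE about 0.115) in every data set for 5 to 30 centres.

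**The case against.** **The estimate does not vanish.** A reader might infer that no risk ratio would be available. That is not supported: in constrained fits under strong covariates the treatment risk ratio was finite in every trial, averaging 1.37, 1.39 and 1.33 for 8, 15 and 25 centres against a true 1.43. What fails is routine convergence and the ordinary Wald interval.

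**Centre may be meant as random.** The primary row says so, and carrying that over to the 6-month row is a natural reading. The high shares in the table then do not describe the model. This stands, but shrinkage removes the problem only when centre variation is small.

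**The size rests on inputs outside the SAP.** The fixed-centre shares at 35% vs 50% run from 0% to 100% depending on centres and covariates, and the 6-month rates are borrowed from 3 months. This stands. A reader might infer near-certain failure, which holds only with many centres and strong covariates.

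**The other rows.** A reader might infer that the tolerance analyses will also fail, or that hospital mortality is safe because death is less common. Neither follows. The SAP gives no rates for these outcomes, and the low-rate results range from 0% to 89%. The tolerance outcomes are tertiary and receive no p-value under section 3.1.

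**The text already names other models.** If sections 5.2.2 and 5.2.3 prevail, the log-binomial model drops out for 6-month mRS and tolerance. This stands, and makes reconciling text and table part of the remedy.

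**A one-line fallback would do.** It would help. But where the first model often fails, the fallback becomes the analysis, so it is cleaner to name a method that works.

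**Blinding limits the harm.** Section 2.4 delays unblinding until primary and secondary analyses are complete, so a model change for 6-month mRS could be made with allocation masked. That reduces the risk of a biased choice but does not make the choice prespecified.

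**Conclusion.** The point holds for 6-month mRS: its Table 1 model can often have no interior solution at the SAP's own planning rates, and nothing says what happens then. With centre fixed, the risk is material from 5 to 10 centres if WFNS and consciousness are strongly prognostic, and from about 15 centres even if they are weak. This assumes that mRS is dichotomised at 2 or below with 6-month rates near the 3-month figures, and it rests on the assumed centre counts, odds ratios and centre variation. A random centre effect would lower the risk by an amount that depends on centre variation.

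For hospital mortality, haemodynamic intolerance and dysnatraemia the same model is named, but the size of the risk cannot be judged from the SAP. The sample size is unaffected. The primary outcome has its own model wording in Table 1 and section 5.2.1 and is not judged here. This should be corrected before database lock; it does not threaten the trial's main conclusion.

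**What to change.** 1. In the Table 1 rows for 6-month mRS, hospital mortality, haemodynamic intolerance and dysnatraemia, replace the log-binomial model by logistic regression with the same covariates. Standardise the predicted risks over the trial population to give the adjusted risk ratio and risk difference, with delta-method or bootstrap 95% confidence intervals.
2. State, before unblinding and preferably before database lock, how centres with no events or only events are pooled. With unequal centres, at least one such centre occurred in 16%, 57% and 95% of simulated trials (8, 15 and 25 centres, 300 trials each). A fixed-centre logistic model then has infinite centre coefficients, although standardised risks can still be computed. Also say whether centre is fixed or random in these rows.
3. Align Table 1 with section 5.2.2 (proportional odds for 6-month mRS; Cox models for mortality) and section 5.2.3 (logistic for tolerance), so that each outcome has one main analysis.

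The cost is a wording change in the SAP and a few lines of code. The risk ratio and the covariates are kept, and no new data are needed.
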